10.4 Intervention after Discharge

Following discharge, a total of 7 telephone contacts at weeks 1, 2, 4, 6, 8, 10, and 12 will be made by the TELE counselor to all participants randomly assigned to the TCG. Each contact will follow the scripted procedure outlined in the Counselors Manual. The same procedure will be followed upon each contact. Up to 3 attempts will be made to contact the participant for each of the 7 scheduled calls, regardless of the outcome of the previously scheduled call.

Unless consent to participate is expressly revoked by the individual, he or she will continue to be contacted as scheduled. Attempts to contact the participant and the outcome of the call will be recorded on the participant contact form in the CRF. The SCG participants will not be contacted by the TELE counselor following their pre-discharge session.

A portion of calls will be recorded and at least 10% of successful calls will be randomly selected and scored for fidelity to the intended call procedures. Each node supervisor will provide supervision to the TELE counselor, per standard practice for the particular program.

In order to provide standardization across all TCG calls, the TELE Counselors Manual provides directions for conducting these calls. Information obtained during the course of the call will not be used as research data with the exception of serious adverse events. These events disclosed by the participant will be documented and reported as described in section 12.0.

The manual also provides minimal instructions for handling medical emergencies such as suicidal threats. Each facility is expected to have a written plan in place for emergency situations. If a plan is not in place, a procedure will be developed by the facility and should be available for review by the node quality assurance (QA) monitor prior to enrollment. Each facility has the responsibility for training its research staff on the facility's emergency plan.

10.5 Participant Initiated Contacts Between Discharge and Follow-Up Visit

If a TCG or SCG participant initiates contact with the original residential program and/or a TELE research staff member after discharge, he or she will be referred to the appropriate program staff member. If there is a change of locater information, the research staff will ensure that the information is updated on the participant's locater form. Additionally, the research staff will maintain a log of any study participant contacts made between discharge and the 13-week follow-up visit. Subsequently, they will be asked to provide this information to the Lead Node.

10.6 Week 13 Follow-Up

10.6.1 Week 13 Follow-Up Visit

At week 13 post-discharge, all participants will meet face-to-face with the designated research assistant from the CTP. There is a 4-week window of opportunity for the 13-week follow-up visit. The follow-up visit should document the following:

- 1. CTN Addiction Severity Index-Lite Follow-up Version 1
- 2. HIV Risk Behavior Survey (RBS)
- 3. Breath alcohol test
- 4. Urine sample collection for drug screen
- 5. Continuing Care Compliance Form
- 6. Serious adverse events
- 7. Study Completion Report (SCR)
- 8. Additional signed program-specific release form if participant attended a program that was not specified on the continuing care plan

If there is difficulty contacting the participant to schedule and/or confirm the 13-week visit, the research assistant may need to look at residential program records for possible updated locator information.

If the research assistant is informed by the participant of an emergency situation during the call to schedule the visit or during the follow-up visit, the research assistant will intervene per the facilities emergency plan.

10.6.2 Verification of Continuing Care Compliance after Follow-up Visit

After completion of the 13-week follow-up visit, participation in continuing care will be verified, where feasible, by confirming attendance/participation in the assigned program as identified on the continuing care (discharge) plan.

In order to verify this information, participants will be asked to sign a program-specific release form at the pre-discharge interview. If the participant attended a program that was not specified on the continuing care plan, an additional program-specific release form will be obtained during the follow-up visit. Attendance and participation in at least one counseling session will be recorded on the follow-up CRF.

Additionally, if approved by the local IRB, the research staff may confirm the participant's self-reported information on criminal justice activity by using the release signed at the pre-discharge interview and/or reviewing public records (e.g., court records, arrest logs, probation and parole records).

10.6.3 Verification of Continuing Care Compliance for Missed Follow-up Visit

If the follow-up visit is missed (e.g., the participant is a 'no-show'), the research staff will use release forms signed at the pre-discharge interview to verify attendance and

participation in the continuing care activities as identified in the residential program's continuing care plan. Additionally, if approved by the local IRB, the research staff may use the release signed at the pre-discharge interview to verify self-reported criminal justice activity that occurred after discharge from the residential facility.

10.7 Participant Compensation

Participants will be compensated \$25 in scrip or cash by the residential program for the time spent in providing the baseline data; each participant will also receive \$25 in scrip or cash by the research assistant at the 13-week follow-up visit for the time spent in the interview. Each CTP will determine the type of scrip most appropriate for its site. All compensation offered must be listed in the ICF and must be approved by the local IRB.

10.8 Participant Withdrawal

Participants are free to withdraw from participating in the study at any time. If they withdraw during the course of the study, they should be encouraged to complete the follow-up assessments that are expected to be obtained at the 13-week follow-up visit.

The principal investigators from each node retain the right to withdraw a participant from the study if the participant is determined to be a threat to self, staff, or other participants. Those participants who are withdrawn from the study by administrators will be provided appropriate referrals to alternative treatments in the area.

All participants randomized to one of the treatment conditions will be included in the data analysis regardless of their subsequent compliance with study procedures. Hence, any randomized participant who withdraws, discontinues, and/or is lost-to-follow should not be replaced.

10.9 Study Outline and Timeline

Table 1 summarizes the step-by-step study schedule and procedures. Steps must be followed within the indicated time intervals. Table 2 provides a timeline of the study.

[figure not shown]
Table 1: Study Outline

Activities During Residential Treatment						
	Activity	Time Interval	Responsible Staff			
Inpatient tr	eatment admission	Program day 1	Residential program intake staff			
Recruitmer Informed continued (must be obtained		Program day 1–7	Research assistant			
Completion assessment	n of baseline s	Program day 1–7*	Research assistant			
Initiation of continuing		Program day 1–7	Residential program staff			
	Variable Reside	ential Stay (7–42 Days)				
Pre-dischar	ge interview	Discharge minus 2 days†	Research assistant			
	continuing care ndomization	Discharge minus 2 days†	TELE counselor			
	Activities Follow	wing Discharge From Residen	tial Treatment			
Week	12-Week T	Γelephone Contact Schedule fo	or TCG Only			
1	TELE call 1	Discharge + 4–10 days	TELE counselor			
2	TELE call 2	Discharge + 11–17 days	TELE counselor			
4	TELE call 3	Discharge + 25–31 days	TELE counselor			
6	6 TELE call 4 Discharge + 39–45 days		TELE counselor			
8 TELE call 5		Discharge + 53–59 days	TELE counselor			
10 TELE call 6		Discharge + 67–73 days	TELE counselor			
12 TELE call 7 D		Discharge + 81–87 days	TELE counselor			
Week	Week Post-Intervention Activities for Both Groups					
13–17	Follow-up data collection	Day of discharge + 88–116 days	Research assistant			

^{*} As close as possible to the date of the participant's admission to the residential facility, ideally within the first 7 business days after admission.

[†] As close as possible to the date of the participant's planned discharge, ideally within the 2 business days prior to planned discharge or on the actual day of discharge.

Table 2: Study Timeline Algorithm

11.0 ASSESSMENT METHODS

11.1 Screening Form

The Screening Form will be completed on all patients consented for participation in the TELE protocol. Initially, it may serve as a guide to recruit participants for the study.

11.2 Locator Form

A Locator Form will be completed by each consented participant and will be kept confidential in the participant's records. Data collected on the Locator Form will be used to facilitate contact with the participant for the follow-up aspects of the project.

Participants will be asked to provide locator information, including a residential street address, working telephone number, driver's license and social security numbers, as well as the addresses and phone number of individuals who may know of their whereabouts. Additionally, participants will be asked to provide the name, address, and phone number of an individual who may be contacted in the event of an emergency. The information will be collected at baseline and reviewed and updated by the research assistant during the participant's pre-discharge interview, prior to randomization.

11.3 HIV Risk Behaviors Survey

The Risk Behavior Survey (RBS), an abbreviated version of the Risk Behavior Assessment (RBA) developed by NIDA for the Cooperative Agreement, will be used to measure risk behaviors related to human immunodeficiency virus (HIV) and hepatitis C virus (HCV). Risk behaviors in the areas of drug use and sex in the previous 30 days are measured. Reliability and validity assessments of the RBS support its adequacy as a research tool for populations of drug users, including intravenous drug users (Darke et al., 1991; Weatherby et al., 1994; Needle et al., 1995).

11.4 CTN Addiction Severity Index-Lite Version 1 and Follow-up Version 1

The CTN Addiction Severity Index-Lite Version 1 and Follow-up Version 1 forms are multidimensional, semi-structured, comprehensive clinical interviews, which provide clinical information important for formulating treatment plans, as well as problem severity profiles in 6 domains commonly affected in substance abusers (McLellan et al., 1985). The domains covered are chemical abuse (alcohol and drug), medical, psychiatric, legal, family/social relations, and employment/support status. Composite scores for each problem domain are derived mathematically and used as change measures or outcome indicators as a function of treatment intervention.

These instruments also provide clinically necessary information on whether the participant is at imminent risk for suicide, thus permitting evaluators to implement any

needed immediate and/or early intervention strategies. The CTN ASI - Lite forms will be administered by a research staff member with a bachelor's degree in the social sciences or equivalent training and experience, as determined by the site's investigator. Composite scores will be calculated according to the procedures described by McGahan et al. (1982), and Carroll et al. (1994).

The CTN ASI - Lite Version 1 form will be administered during the baseline assessment and the CTN ASI - Lite Follow-up Version 1 will be administered at the 13-week follow-up visit.

11.5 Randomization Form

Prior to randomization, through review of the Randomization Form, the research assistant will confirm the participant's eligibility for randomization. If the participant remains eligible, the subject will be randomized and the treatment group assignment will be recorded on this form. If the participant is not randomized, the reason for ineligibility for randomization will be captured on this form as well.

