10.3 Study Assessments Prior to Discharge

10.3.1 Pre-Discharge Interview

All participants will receive their program's routine continuing care plan (discharge plan), developed by their residential counselor or developed as usual at the specific treatment program.

All participants will meet with the research assistant prior to randomization as close as possible to the date of the participant's planned discharge, ideally within the 2 business days prior to the planned date of discharge or on the actual day of discharge. At the meeting, the research assistant will do the following:

1. Review the consent form signed by the participant to assure that the participant continues to understand and be a willing participant in the TELE study

- 2. Review the locater form previously completed by the participant and update as needed
- 3. Discuss the week-13 post-residential program follow-up visit:
 - a. Describe the visit (participant will be expected to answer questions, provide a urine sample, and perform a breath alcohol test).
 - b. Attempt to schedule the date, time, and the location of this visit. The participant should be given an appointment card (or equivalent) with the agreed-upon date for the follow-up visit.
 - c. Provide each participant with contact information for the research assistant who will conduct the follow-up visit, in case the participant needs to reschedule the week 13 visit and the locater information changes during the 13 weeks following discharge.
 - d. Obtain signed release form(s) for program(s) to which the participant is referred for post-discharge continuing care activities in order to verify compliance and release form(s) for arrest and conviction records to possibly verify self-reported criminal justice activity that occurred after discharge from the residential facility.

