10.3.2 Review of the Continuing Care Plan and Randomization

All participants will meet with the TELE counselor prior to randomization as close as possible to the date of the participant's planned discharge, ideally within the 2 business days prior to the planned date of discharge or on the actual day of discharge, to review the continuing care plan. If a thorough review has been performed by the residential program counselor, the TELE counselor only needs to ensure participant comprehension of this plan. Subsequently, the TELE counselor will perform the manual randomization (of participants remaining eligible) to either telephone counseling calls (TCG) or standard of care (SCG). This will be done as close as possible to the date of the participant's planned discharge, ideally within the 2 business days prior to the planned date of discharge or on the actual day of discharge.

A set of envelopes, numbered sequentially and provided to each site prior to the recruitment of participants, will be used to determine a participant's random assignment. At the time of randomization, the TELE counselor will remove the envelope with the next sequential number. Upon opening the envelope, the TELE counselor will inform the participant of the group to which he or she is randomized. If the participant is randomized to SCG, the TELE counselor should remind the participant of his or her planned continuing care and the 13-week visit, and conclude the meeting. If the participant is randomized to the TCG, the TELE counselor should schedule the first call during this meeting. The participant should be reminded of his or her planned continuing care and the week 13 follow-up visit, and the interview should be concluded. Refer to the Counselors Manual for more details.

The goal of this pre-discharge meeting is to establish rapport with all study participants to avoid bias of the study results, which might occur if only the group randomized to follow-up phone calls had had the pre-discharge meeting.

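### The week 13 assessor is not masked, and section 11.5 records the arm on a form that the assessor's role reviews, although only the TELE counselor and the participant need it

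*Protocol*

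**What the plan says.** All references are to the protocol.

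- **Before randomization (11.5):** "through review of the Randomization Form, the research assistant will confirm the participant's eligibility for randomization". Section 10.2 also lists this form among those completed at baseline.
- **At randomization (11.5):** "the subject will be randomized and the treatment group assignment will be recorded on this form". The person who records the arm is not named.
- **Who learns the arm (10.3.2):** "Upon opening the envelope, the TELE counselor will inform the participant of the group to which he or she is randomized". Table 1 gives randomization and all seven calls to the counselor.
- **Call records (10.4):** "the outcome of the call will be recorded on the participant contact form in the CRF". Section 11.8 limits this form to the telephone group (TCG) and describes it as a record of the counselor's attempts.
- **Week 13 (10.6.1):** "all participants will meet face-to-face with the designated research assistant from the CTP". If contact is difficult, "the research assistant may need to look at residential program records for possible updated locator information". Sections 11.6, 11.7 and 11.10 give urine collection, the breath test and the eliciting of SAEs to the same role.
- **Same person or not (10.3.1):** the participant receives "contact information for the research assistant who will conduct the follow-up visit", which leaves open whether that is the assistant who checked eligibility.
- **Masking:** blinding is mentioned only for SAE reports (12.3.3.3) and interim SAE listings (13.4). No sentence masks the week 13 assessor.

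**The concern.** The protocol already separates the two roles that a masked assessment needs: one person randomizes and calls, another measures. It makes no use of that separation. Eligibility and arm share one form, and no instruction keeps the completed form from the assistant.

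An assessor who knows the arm could affect the comparison in three places:

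- Self-reported aftercare engagement is one of the three main efficacy measures in 13.3 and is collected at this visit.
- The ASI-Lite forms are described in 11.4 as "multidimensional, semi-structured, comprehensive clinical interviews", so probing involves some judgement.
- Effort in reaching people affects who is counted as lost, and the first abstinence analysis in 13.3.1 treats the lost as non-abstinent.

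The study is exploratory, but 5.1 lists the effect size among the critical aspects of feasibility and intends it for the power calculation of a later trial. A biased estimate would carry over. Section 10.3.2 also shows that the authors had this kind of bias in mind: everyone meets the counselor before discharge so that the meeting itself does not separate the arms.

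**Working it through.** **Tracing the roles.** The protocol gives no figure to reproduce on this point, so the check follows each role through the text.

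| Step | Role | Needs the arm? |
|---|---|---|
| Baseline, pre-discharge interview, eligibility check (10.2, 10.3.1, 11.5) | Research assistant | No, not yet assigned |
| Envelope, telling the participant (10.3.2) | TELE counselor | Yes |
| Recording the arm on the Randomization Form (11.5) | Not named | – |
| Calls, contact form (10.4, 11.8) | TELE counselor | Yes |
| Scheduling, tracing, week 13 visit (10.6.1) | Research assistant | No |

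One further route is indirect. Section 11.10 has SAEs entered at week 13 only if they have not been recorded before. That suggests sight of earlier SAE pages, and a page that arose from a scheduled call can exist only in TCG.

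**Scale of the tracing route.** Inputs from the protocol: 180 per arm (3.0), loss of 20% or fewer (13.3.1), lost counted as non-abstinent (13.3.1). Assumptions: true abstinence a is equal in both arms, being traced is unrelated to abstinence, overall loss is exactly 20%, and the test is at a nominal two-sided 0.05 (the protocol sets no level).

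Apparent abstinence in an arm is a × f, where f is the fraction traced. The spurious difference is d = a × (f_TCG − f_SCG). The probability of rejecting in favour of TCG is Φ{[d − 1.96·√(2p̄(1−p̄)/180)] / √[(p₁(1−p₁)+p₂(1−p₂))/180]}.

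Example with a = 0.5 and tracing of 85% and 75%: p₁ = 0.425, p₂ = 0.375, d = 0.05. The two standard errors are 0.0516 and 0.0516, so Φ[(0.05 − 0.101)/0.0516] = 0.16.

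| Traced TCG / SCG | d for a = 0.4 to 0.6 | Probability of rejecting for TCG |
|---|---|---|
| 80% / 80% | 0 | 0.025 |
| 82.5% / 77.5% | 2–3 points | 0.06–0.08 |
| 85% / 75% | 4–6 points | 0.13–0.21 |
| 90% / 70% | 8–12 points | 0.37–0.63 |

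Under the same assumptions, the second analysis in 13.3.1 (lost treated as missing) compares a with a and shows no spurious difference.

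**Scale of the interview route.** With 180 × 0.8 = 144 seen per arm, the standard error of a standardized difference is √(2/144) = 0.118. An assessor-induced shift of 0.1, 0.2 or 0.3 SD would reach nominal two-sided 0.05 with probability 0.13, 0.40 or 0.72. The shifts are assumed; the protocol supports no particular value.

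**The case against.** The strongest reply is that the protocol does not say the assessor sees the arm. The assistant's review in 11.5 comes before randomization, when there is no arm to see. The assignment is recorded in the passive voice, and since the counselor performs randomization, the counselor may well be the one who writes it down. The contact form records the counselor's attempts, and nothing gives it to the assistant. The week 13 assistant may be someone else, and form handling may be set in the Operations Manual or Counselors Manual, which are not at hand.

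All of that stands. A reader might infer that form routing definitely unmasks the assessor, or that the assistant handles the contact pages; the text supports neither as fact. What remains is that the arm goes onto a form this role works with, and no sentence keeps it from the person who measures the outcomes.

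It can also be said that two of the three main measures are urine and breath tests, that ASI composites are calculated, that assistants are trained with the goal of certification (15.1), and that 13.3.1 compares the number missing between arms. These narrow the exposure. They do not protect the self-reported main measure, and the missing-data comparison would show unequal tracing without preventing it.

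Finally, efficacy is secondary and no significance level is set. This lowers the weight of the point but does not remove it, because effect size is itself a listed feasibility aim.

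**Conclusion.** The point holds as a gap in masking that is cheap to close. The week 13 assessor is not masked, and 11.5 places the arm on a form that the assessor's role reviews, when only the counselor and the participant need it.

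The size of any bias is unknown. The figures above show what unequal tracing or shifted scoring would do if they occurred; they do not show that either would. It would be tempting to express a 0.1–0.2 SD assessor shift as a share of a 0.2 SD true effect, but both numbers would be chosen, so the ratio says nothing about this trial. Section 5.1 asks for sufficient and equivalent follow-up data but does not add that equivalence is meant by arm, so that aim should not be pressed further than its wording.

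The exposure lies mainly in self-reported engagement, the ASI-Lite and tracing. The urine and breath results themselves are much less open to it. This is a should-fix for an exploratory study whose effect size is meant to inform a larger one.

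**What to change.** - **10.6:** state that the week 13 assessor is to be kept unaware of the arm.
- **11.5:** end the research assistant's part of the Randomization Form at confirmation of eligibility. Have the TELE counselor record the assignment on a separate page sent directly to the Data Management Center.
- **Filing:** keep that page, the TCG contact forms and the SAE pages that arise from calls apart from the research assistant. Adjust 11.10 to match, so that SAE duplicates are reconciled at the Data Management Center instead of at the visit. The reporting duties in 12.3.3.3 stay as they are.
- **Week 13 visit:** ask participants at the start not to mention calls. After the outcome measures, have the assistant record whether the arm became known.

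The cost is a little form routing, one CRF item and some SAE reconciliation, with existing staff and no added visits. Masking will be partial, because participants know their arm and can disclose it, and their own reporting may differ by arm whatever the routing. The recorded item would at least show how often masking failed, which is useful to know before a full trial.
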